### **7.2 Study Schedule**

#### **7.2.1 Screening**

In the following, procedures and evaluations necessary for assessing whether a participant meets eligibility criteria are described:

- In case a physician's patients is suspected of having a UGIB and endoscopy is scheduled, an investigator is contacted and introduced to the patient. A physician might also be an investigator.
- Patient information is provided. Any questions a patient may have, are answered. Informed patient consent is obtained. The patient is made aware that he or she may withdraw from trial participation at any time.

- Inclusion and exclusion criteria are applied to further investigate a patient's eligibility for trial participation.
- Screening is concluded and the patient is enrolled.

## 7.2.2 Enrollment

If a patient is successfully screened and informed consent obtained, he or she is enrolled into the trial. As endoscopy is already scheduled, a trial participant likely stays at the hospital. Approximately 20 to 60 minutes prior to endoscopy, the HemoPill acute capsule is activated by the investigator and a data connection to the HemoPill Receiver is established. Then, the HemoPill acute capsule is ingested by the trial participant with a minimal amount of water.

## 8 Assessment of Safety

### 8.1 Specification of Safety Parameters

Safety parameters are identical to the safety endpoints defined in chapter 4.2.2:

Adverse events / complications associated with trial or control procedure, such as:

Trial procedure:

- Aspiration of the capsule on ingestion
- Delayed excretion, or failure to excrete the capsule (capsule retention)
- Obstruction of the digestive tract
- Injury to tissue structures during the passage of the HemoPill acute through the digestive tract.

Control procedure:

- Cardiopulmonary adverse events
- Infection
- Perforation
- Bleeding

#### 8.1.1 Definition of Adverse Events (AE)

An *adverse event* (AE) is any symptom, sign, illness or experience that develops or worsens in severity during the course of the study. Intercurrent illnesses or injuries should be regarded as adverse events. Abnormal results of diagnostic procedures are considered to be adverse events if the abnormality:

- results in study withdrawal
- is associated with a serious adverse event
- is associated with clinical signs or symptoms
- leads to additional treatment or to further diagnostic tests
- is considered by the investigator to be of clinical significance

#### 8.1.2 Definition of Serious Adverse Events (SAE)

##### Serious Adverse Event

Adverse events are classified as serious or non-serious. A *serious adverse event* is any AE that is:

- fatal
- life-threatening
- requires or prolongs hospital stay
- results in persistent or significant disability or incapacity
- an important medical event

Important medical events are those that may not be immediately life threatening, but are clearly of major clinical significance. They may jeopardize the subject, and may require intervention to prevent one of the other serious outcomes noted above. For example, drug overdose or abuse, a seizure that did not result in in-patient hospitalization, or intensive treatment of bronchospasm in an emergency department would typically be considered serious.

All adverse events that do not meet any of the criteria for serious should be regarded as ***non-serious adverse events***.

### **8.1.3 Definition of Unanticipated Problems (UP)**

#### **Unanticipated Problems Involving Risk to Subjects or Others**

Any incident, experience, or outcome that meets all of the following criteria:

- Unexpected in nature, severity, or frequency (i.e. not described in study-related documents such as the IRB-approved protocol or consent form, the investigators brochure, etc)
- Related or possibly related to participation in the research (i.e. possibly related means there is a reasonable possibility that the incident experience, or outcome may have been caused by the procedures involved in the research)
- Suggests that the research places subjects or others at greater risk of harm (including physical, psychological, economic, or social harm).

This definition could include an unanticipated adverse device effect, any serious adverse effect on health or safety or any life-threatening problem or death caused by, or associated with, a device, if that effect, problem, or death was not previously identified in nature, severity, or degree of incidence in the investigational plan or application (including a supplementary plan or application), or any other unanticipated serious problem associated with a device that relates to the rights, safety, or welfare of subjects (21 CFR 812.3(s)).

## **8.2 Classification of an Adverse Event**

### **8.2.1 Severity of Event**

For AEs not included in the protocol defined grading system, the following guidelines will be used to describe severity.

- **Mild** – Events require minimal or no treatment and do not interfere with the participant's daily activities.
- **Moderate** – Events result in a low level of inconvenience or concern with the therapeutic measures. Moderate events may cause some interference with functioning.
- **Severe** – Events interrupt a participant's usual daily activity and may require systemic drug therapy or other treatment. Severe events are usually potentially life-threatening or incapacitating.

### **8.2.2 Relationship to Study Agent**

*The clinician's assessment of an AE's relationship to subject device is part of the documentation process, but it is not a factor in determining what is or is not reported in the study. If there is any doubt as to whether a clinical observation is an AE, the event should be reported. All AEs must have their relationship to subject device assessed. In a clinical trial, the study product must always be suspect. To help assess, the following guidelines are used.*

- **Related** – *The AE is known to occur with the subject device, there is a reasonable possibility that the subject device caused the AE, or there is a temporal relationship between the subject device and event. Reasonable possibility means that there is evidence to suggest a causal relationship between the subject device and the AE.*
- **Not Related** – *There is not a reasonable possibility that the use of the subject device caused the event, there is no temporal relationship between the subject device and event onset, or an alternate etiology has been established.*

### 8.2.3 Expectedness

Expected adverse reactions known to occur for capsule endoscope devices and complications associated with the control procedure endoscopy are:

Trial procedure:

- Aspiration of the capsule on ingestion
- Delayed excretion, or failure to excrete the capsule (capsule retention)
- Obstruction of the digestive tract
- Injury to tissue structures during the passage of the HemoPill acute through the digestive tract. In particular, this may involve:
  - Injury to the mucosa
  - Bleeding, e.g., variceal bleeding
  - Perforations

Control procedure:

- Cardiopulmonary adverse events
- Infection
- Perforation
- Bleeding

[name] will be responsible for determining whether an AE is expected or unexpected. An AE will be considered unexpected if the nature, severity, or frequency of the event is not consistent with the risk information previously described for the subject device.

### 8.3 Time Period and Frequency for Event Assessment and Follow-Up

AEs and SAEs from trial procedure:

- Aspiration of the capsule on ingestion  
Immediate identification through extensive coughing. Localization and retrieval with bronchoscope.
- Delayed excretion, or failure to excrete the capsule (capsule retention)  
Identification
- Obstruction of the digestive tract
- Injury to tissue structures during the passage of the HemoPill acute through the digestive tract. In particular, this may involve:
  - Injury to the mucosa
  - Bleeding, e.g., variceal bleeding
  - Perforations

## **8.4 Reporting Procedures – Notifying the IRB**

### **8.4.1 Adverse Event Reporting**

SAEs as defined above, and any adverse events related to the study device (AI) should be reported within 24 hours of the Investigator's knowledge of the event to Sponsor as well as IRB department. Reporting to the IRB will be performed by the Investigator

### **8.4.2 Serious Adverse Event Reporting**

All SAEs, unless otherwise specified in the protocol and approved by the IRB, require expedited reporting by the Principal Investigator to the study's safety monitoring bodies. An expedited report of an SAE can be submitted by telephone, fax, or email and must be reported to the independent safety monitoring body within 24 hours of the event being reported to the Investigator. The expedited report should be followed by a detailed, written SAE report as soon as possible. Follow up information may be required and asked for by the independent safety monitoring body directly. If a second serious event occurs, the study will be halted.

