## **8.5 Reporting Procedures – Notifying the Study Sponsor**

The study clinician will complete a SAE Form within the following timelines:

- All deaths and immediately life-threatening events, whether related or unrelated, will be recorded on the SAE Form and submitted to the IRB office and [name] within 24 hours of site awareness. See Section 1, Key Roles for contact information.
- Other SAEs regardless of relationship will be submitted to the [name] within 72 hours of site awareness.

All SAEs will be followed until satisfactory resolution or until the site investigator deems the event to be chronic or the adherence to be stable. Other supporting documentation of the event may be requested by the [name] and should be provided as soon as possible.

As a follow-up to the initial report, within the following 48 hours of awareness of the event, the investigator shall provide further information, as applicable, on the unanticipated event or the unanticipated problem in the form of a written narrative. This should include a copy of the completed Unanticipated Problem form, and any other diagnostic information that will assist the understanding of the event. Significant new information on ongoing unanticipated adverse effects shall be provided promptly to the study sponsor.

The study investigator shall complete an Unanticipated Adverse Device Effect Form and submit to the study sponsor and to the reviewing IRB as soon as possible, but in no event later than 10 working days after the investigator first learns of the effect. The study sponsor contact information is provided in Section 1, Key Roles.

As a follow-up to the initial report, within the following 48 hours of awareness of the event, the investigator shall provide further information, as applicable, on the unanticipated event or the unanticipated problem in the form of a written narrative. This should include a copy of the completed Unanticipated Problem form, and any other diagnostic information that will assist the understanding of the event. Significant new information on ongoing unanticipated adverse effects shall be provided promptly to the study sponsor.

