### ***8.6 Study Halting Rules***

Use of subject device will be halted when three grade 3 AEs determined to be “probably related” are reported to the, [name]. [name] will notify the study sponsor and investigators immediately when the third grade 3 event is reported and enrollment screens will stop accepting new study participants. The study sponsor will inform the DSMB members within 24 hours of this occurrence and will provide the DSMB with AE listing reports. The DSMB will convene an ad hoc meeting by teleconference or in writing as soon as possible. The DSMB will provide recommendations for proceeding with the study to the study sponsor.

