### ***8.7 Safety Oversight***

Data Safety Monitoring will be conducted by [name], who is a board-certified gastroenterologist trained in endoscopic procedures including upper endoscopy. Data safety monitoring will be done after each cohort of 10 patients is enrolled.

SAE and AE are defined as:

- Aspiration of the capsule on ingestion  
Immediate identification through extensive coughing. Localization and retrieval with bronchoscope.
- Delayed excretion, or failure to excrete the capsule (capsule retention)  
Identification
- Obstruction of the digestive tract

- Injury to tissue structures during the passage of the HemoPill acute through the digestive tract. In particular, this may involve:
  - Injury to the mucosa
  - Bleeding, e.g., variceal bleeding
  - Perforations

Furthermore, unexpected events are classified as SAE or AE under consideration of the respective definitions provided in chapter 8.1.1 and chapter 8.1.2

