#### **10.4.4 Safety Analyses**

Among the secondary endpoints, safety endpoints are defined (see chapter 4.2.2). Occurrences are documented, and their respective prevalence is calculated and described in relation to the total number of participants. Safety oversight measures are described in chapter 8.7. The Study will be halted after two SAEs (see chapter 8.4.2).

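### The halting rules in 8.4.2 and 10.4.4 (two SAEs) and in 8.6 (three grade 3, probably related AEs) are not reconciled, and the 8.6 trigger uses categories that 8.2 does not define

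*Combined protocol and SAP*

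**What the plan says.** The combined protocol and SAP sets a halting condition in three places.

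- **8.4.2 (SAE reporting):** "If a second serious event occurs, the study will be halted". There is no condition on relatedness or severity grade.
- **10.4.4 (safety analyses):** "The Study will be halted after two SAEs", with a cross-reference to 8.4.2 and none to 8.6.
- **8.6 (study halting rules):** "Use of subject device will be halted when three grade 3 AEs determined to be" probably related. Notification then follows "immediately when the third grade 3 event is reported and enrollment screens will stop accepting new study participants", and a DSMB makes a recommendation on proceeding. The two-SAE rule is not mentioned.

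The terms and reporting routes that feed these rules are set elsewhere.

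- **8.1.2** defines an SAE by general seriousness criteria, whatever the cause.
- **8.2.1** grades severity as mild, moderate or severe. It mentions a protocol-defined grading system that does not appear in the text.
- **8.2.2** rates causality as related or not related.
- **8.4.1** sets the first reporting time: "SAEs as defined above, and any adverse events related to the study device (AI) should be reported within 24 hours", to the sponsor and the IRB.
- **8.5** is headed as sponsor notification. It sets 24 hours for deaths and immediately life-threatening events, and a longer time for the rest: "Other SAEs regardless of relationship will be submitted to the" recipient (name removed) within 72 hours.
- **8.7** describes review by a gastroenterologist: "Data safety monitoring will be done after each cohort of 10 patients is enrolled". It also says that SAEs and AEs are defined as a list of capsule events, then adds unexpected events classified under 8.1.1 and 8.1.2.

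**The concern.** A halting rule has to give one answer on the day of the event. Here the threshold (two or three), the type of event (SAE or grade 3 AE), the attribution (none stated or probably related) and the thing halted (the study, or device use and enrollment) all differ between sections, and nothing joins them. In a single-arm study where every participant swallows the capsule, halting device use stops the trial in practice, so the difference in what is halted does not separate the rules much.

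The investigator, the safety monitor and the IRB could each cite a different section for the same events. Participant protection is at stake first. The orderly conduct of a 50-patient study is also at stake, because complications of the endoscopy are themselves safety endpoints (4.2.2) and an SAE unrelated to the capsule is therefore foreseeable.

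**Working it through.** The documents state no operating characteristic for either rule, so there is no planned figure to reproduce. The check is mainly a comparison of the text.

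**1. The two triggers side by side**

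| | 8.4.2 and 10.4.4 | 8.6 |
|---|---|---|
| Count | 2 | 3 |
| Event | SAE | grade 3 AE |
| Relatedness | none stated | probably related |
| What is halted | the study | device use and new enrollment |
| Next step | none given there | DSMB recommendation |

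**2. A case where they diverge.** Take two events that are serious, severe and device-related. Under 8.4.2 and 10.4.4 the second requires a halt. Under 8.6 the count is at most two, so its trigger is not met even if severe is read as grade 3 and related as probably related.

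**3. Can 8.6 be evaluated from the data collected?** It needs a numeric grade and a graded causality level. Section 8.2.1 has three verbal severity levels and no numbers. Section 8.2.2 has two causality levels and no intermediate one. No mapping is given, so the trigger rests on undefined terms.

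**4. Which SAEs count under 8.4.2?** Section 8.1.2 is independent of cause, and 8.5 collects SAEs regardless of relationship. Section 8.7 instead defines SAE and AE through a capsule-event list plus unexpected events. An expected endoscopy complication that meets 8.1.2 is an SAE under 8.1.2 but is not on the 8.7 list.

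**5. Reporting time.** The 24 hours in 8.4.2 runs to the safety monitoring body, so it does not itself conflict with 8.5. The direct conflict is 8.4.1 (24 hours to sponsor and IRB, all SAEs) against 8.5 (72 hours for SAEs that are not immediately life-threatening). The recipient's name is removed in 8.5, and the section heading indicates that it is the sponsor.

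**6. Illustration of how easily two SAEs could arise.** Inputs: n = 50 (10.5) and a per-participant SAE risk p = 1/30, from the single SAE, judged unrelated to the device, among 30 patients in the pre-market study (2.2.5). Assuming independent participants with at most one SAE each:

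P(at least 2) = 1 − (1 − p)^50 − 50·p·(1 − p)^49

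= 1 − (29/30)^50 − 50·(1/30)·(29/30)^49 ≈ 1 − 0.184 − 0.317 ≈ 0.50.

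Because one event in 30 is a weak basis, here are lower assumed rates with the same formula: 0.089 at 1%, 0.264 at 2%, 0.445 at 3%.

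No matching probability is given for 8.6. The documents contain no rate for grade 3, probably related AEs. Putting the SAE rate into both rules would compare two with three of the same event, which is not how the rules differ.

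**The case against.** The strongest reply is that these are parallel triggers. They count different events, and 8.6 states when to halt without saying that the study continues below three events. A cautious site could obey both by halting at whichever is met first. That is a possible reading, and it means a reader should not infer that 8.6 gives permission to continue after two SAEs. But no section says that both rules apply, and the section a reader would consult for halting rules omits the two-SAE rule entirely.

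Four further inferences are tempting and are not supported.

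- *The 8.6 trigger can never be met.* Severe is the third of three ordered levels and a reader could apply severe plus related. The supportable charge is that the terms are undefined.
- *Any SAE of any cause counts.* Sections 8.1.2 and 8.5 point that way, but the definition in 8.7 leaves it open.
- *There is no DSMB.* Sections 8.4.2, 8.6 and 8.7 use different descriptions of the oversight body, but the Key Roles section is not in the text available for this review, so its absence cannot be concluded.
- *The 0.50 is the chance of missing 43 evaluable patients.* Section 5.8 allows the study to resume after a suspension, so a halt is not termination.

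The illustration also probably overstates the risk. The pre-market study monitored excretion for up to 4 days, whereas participation here ends with endoscopy (Protocol Summary, 5.5). Against that, 8.3 gives no end to the event collection window, and capsule retention, a later event, is a safety endpoint.

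**Conclusion.** Wrong as written, as an internal inconsistency. Two unreconciled halting conditions stand in the protocol. For two serious, severe, device-related events, one requires a halt and the trigger of the other is not met. The 8.6 trigger has no defined mapping to the 8.2 scales, the set of SAEs that count is unsettled, and the sponsor reporting time differs (24 against 72 hours).

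These conclusions rest on the text alone, except that the reporting-time conflict assumes the removed recipient in 8.5 is the sponsor. The size is illustrative: about a 0.50 chance of at least two SAEs in 50 participants if the 1/30 rate carried over, and 0.089 to 0.445 for assumed rates of 1% to 3%. The primary analysis is not affected. The issue is safety conduct, and which rule is the intended one cannot be settled from the documents.

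**What to change.** Reconcile 8.4.2, 8.6, 8.7 and 10.4.4 into one halting rule, or into two rules that are explicitly joined, stated identically wherever they appear. In doing so:

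- express the rule in the severity and causality categories of 8.2, or define the extra categories there;
- state whether relatedness to the device is required, and use one definition of the SAEs that count across 8.1.2, 8.5 and 8.7;
- use the same name for the oversight body in 8.4.2, 8.6 and 8.7;
- give one SAE reporting time to the sponsor in 8.4.1 and 8.5.

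Which rule and which reporting time apply is for the sponsor, the investigator and the IRB to decide. The cost is a wording amendment with IRB review, with no added patients, staff or procedures.

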### **8.4.3 Unanticipated Problem Reporting**

Unexpected risks will be evaluated throughout the research study and any modifications, based on serious and unexpected adverse events occurring and reported in these submitted reports and not previously identified in this research study, would be implemented by the study team on an ongoing basis. Any serious or unexpected adverse event related to HemoPill will necessitate review with modification of the protocol to address the specific adverse event.

Incidents or events that meet the OHRP criteria for UPs require the creation and completion of an UP report form. It is the site investigator's responsibility to report UPs to their IRB and [name]. The UP report will include the following information:

- Protocol identifying information: protocol title and number, PI's name, and the IRB project number;
- A detailed description of the event, incident, experience, or outcome;
- An explanation of the basis for determining that the event, incident, experience, or outcome represents an UP;
- A description of any changes to the protocol or other corrective actions that have been taken or are proposed in response to the UP.

### **8.4.4 Reporting of Pregnancy**

Pregnant women are excluded from trial participation. As from enrollment to trial intervention merely hours elapse, change in pregnancy status of an enrolled patient is highly unlikely. However, if pregnancy is discovered after trial enrollment, trial participation is terminated.

## **8.5 Reporting Procedures – Notifying the Study Sponsor**

The study clinician will complete a SAE Form within the following timelines:

- All deaths and immediately life-threatening events, whether related or unrelated, will be recorded on the SAE Form and submitted to the IRB office and [name] within 24 hours of site awareness. See Section 1, Key Roles for contact information.
- Other SAEs regardless of relationship will be submitted to the [name] within 72 hours of site awareness.

All SAEs will be followed until satisfactory resolution or until the site investigator deems the event to be chronic or the adherence to be stable. Other supporting documentation of the event may be requested by the [name] and should be provided as soon as possible.

As a follow-up to the initial report, within the following 48 hours of awareness of the event, the investigator shall provide further information, as applicable, on the unanticipated event or the unanticipated problem in the form of a written narrative. This should include a copy of the completed Unanticipated Problem form, and any other diagnostic information that will assist the understanding of the event. Significant new information on ongoing unanticipated adverse effects shall be provided promptly to the study sponsor.

The study investigator shall complete an Unanticipated Adverse Device Effect Form and submit to the study sponsor and to the reviewing IRB as soon as possible, but in no event later than 10 working days after the investigator first learns of the effect. The study sponsor contact information is provided in Section 1, Key Roles.

As a follow-up to the initial report, within the following 48 hours of awareness of the event, the investigator shall provide further information, as applicable, on the unanticipated event or the unanticipated problem in the form of a written narrative. This should include a copy of the completed Unanticipated Problem form, and any other diagnostic information that will assist the understanding of the event. Significant new information on ongoing unanticipated adverse effects shall be provided promptly to the study sponsor.

The PI is responsible for conducting an evaluation of an unanticipated adverse device effect and shall report the results of such evaluation the reviewing IRB and participating investigators within 10 working days after the sponsor first receives notice of the effect. Thereafter the sponsor shall submit such additional reports concerning the effect as IRB requests.

